11.5 Pregnancy

Although not an adverse event in and of itself, pregnancy as well as its outcome must be documented via CTEP-AERS. In addition, the *Pregnancy Information Form* included within the NCI Guidelines for Adverse Event Reporting Requirements must be completed and submitted to CTEP. Any pregnancy occurring in a patient or patient's partner from the time of consent to 90 days after the last dose of study drug must be reported and then followed for outcome. Newborn infants should be followed until 30 days old. Please see the "NCI Guidelines for Investigators: Adverse Event Reporting Requirements for DCTD (CTEP and CIP) and DCP INDs and IDEs" (at http://ctep.cancer.gov/protocolDevelopment/adverse_effects.htm) for more details on how to report pregnancy and its outcome to CTEP.

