3.1.9. Patients with a known history of hepatitis C virus (HCV) infection must have been treated and cured. For patients with HCV infection who are currently on treatment, they are eligible if they have an undetectable HCV viral load. For patients with evidence of chronic hepatitis B virus (HBV) infection, the HBV viral load must be undetectable on suppressive therapy, if indicated.

3.1.10. Patients who have undergone major surgery must have recovered adequately from the toxicity and/or complications from the intervention prior to starting therapy.

3.1.11. Patients with known history or current symptoms of cardiac disease, or history of treatment with cardiotoxic agents, should have a clinical risk assessment of cardiac function using the

New York Heart Association Functional Classification. To be eligible for this trial, patients should be class 2B or better.

- 3.1.12. Female patients of childbearing potential must have a negative urine or serum pregnancy test within 72 hours prior to receiving the first dose of 7+3 treatment. If the urine test is positive or cannot be confirmed as negative, a serum pregnancy test will be required. A female of childbearing potential is any woman, regardless of sexual orientation or whether they have undergone tubal ligation, who meets the following criteria: 1) has not undergone a hysterectomy or bilateral oophorectomy; or 2) has not been naturally postmenopausal for at least 12 consecutive months (*i.e.*, has had menses at any time in the preceding 12 consecutive months).

Female patients of childbearing potential must be willing to use an adequate method of contraception as outlined in Section 6.6 (Contraception and Pregnancy) for the course of the study through 120 days after the last dose of study medication.

Male patients with female partners of childbearing potential must agree to use an adequate method of contraception as outlined in Section 6.6 (Contraception and Pregnancy), starting with the first dose of study therapy through 120 days after the last dose of study therapy.

NOTE: Abstinence is acceptable if this is the usual lifestyle and preferred contraception for the patient.

- 3.1.13. Ability to understand and the willingness to sign a written informed consent document. Participants with impaired decision-making capacity (IDMC) who have a legally-authorized representative (LAR) and/or family member available will also be eligible.

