7.6 Contraception and Pregnancy

7.6.1 Contraception

Pembrolizumab (MK-3475) may have adverse effects on a fetus in utero. Furthermore, it is not known if pembrolizumab (MK- 3475) has transient adverse effects on the composition of sperm.

Based on the mechanism of action and findings from animal reproduction studies, fetal harm may occur if cytarabine is administered during pregnancy. Risk to the fetus is decreased if treatment can be avoided during the first trimester; however, females of reproductive potential should avoid becoming pregnant during treatment and be advised of the potential risks.

Idarubicin: Adverse events were observed in animal reproduction studies. Women of reproductive potential avoid pregnancy during treatment.

Daunorubicin: Adverse events have been observed in animal reproduction studies.

Daunorubicin crosses the placenta. Women of reproductive potential should avoid pregnancy.

For this trial, male patients will be considered to be of nonreproductive potential if they have azoospermia (whether due to having had a vasectomy or due to an underlying medical condition).

Female patients will be considered of nonreproductive potential if they are either:

1. Postmenopausal (defined as at least 12 months with no menses without an alternative medical cause; in women <45 years of age, a high follicle stimulating hormone (FSH) level in the postmenopausal range may be used to confirm a postmenopausal state in women not using hormonal contraception or hormonal replacement therapy. In the absence of 12 months of amenorrhea, a single FSH measurement is insufficient.);
OR
2. Have had a hysterectomy and/or bilateral oophorectomy, or bilateral salpingectomy at least 6 weeks prior to screening.
OR
3. Has a congenital or acquired condition that prevents childbearing.

Female and male patients with female partners of reproductive potential must agree to avoid becoming pregnant or impregnating a partner, respectively, while receiving study drug and for 120 days after the last dose of study drug by complying with one of the following:

1. Practice abstinence[†] from heterosexual activity.
OR
2. Use (or have their partner use) adequate contraception during heterosexual activity.

Acceptable methods of contraception are[‡]:

Single method (1 of the following is acceptable):

- intrauterine device (IUD)
- vasectomy of a female patient's male partner
- contraceptive rod implanted into the skin.

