Combination method (requires use of 2 of the following):

- diaphragm with spermicide (cannot be used in conjunction with cervical cap/spermicide)
- cervical cap with spermicide (nulliparous women only)
- contraceptive sponge (nulliparous women only)
- male condom or female condom (cannot be used together)
- hormonal contraceptive: oral contraceptive pill (estrogen/progestin pill or progestin-only pill), contraceptive skin patch, vaginal contraceptive ring, or subcutaneous contraceptive injection

[†]Abstinence (relative to heterosexual activity) can be used as the sole method of

contraception if it is consistently employed as the patient's preferred and usual lifestyle and if considered acceptable by local regulatory agencies and Ethics Review Committees (ERCs)/Institutional Review Boards (IRBs). Periodic abstinence (*e.g.*, calendar, ovulation, sympto-thermal, post-ovulation methods, etc.) and withdrawal are not acceptable methods of contraception.

‡If a contraceptive method listed above is restricted by local regulations/guidelines, then it does not qualify as an acceptable method of contraception for patients participating at sites in this country/region.

Patients should be informed that taking the study medication may involve unknown risks to the fetus (unborn baby) if pregnancy were to occur during the study. In order to participate in the study, patients of childbearing potential must adhere to the contraception requirement (described above) from the day of study medication initiation (or 14 days prior to the initiation of study medication for oral contraception) throughout the study period up to 120 days after the last dose of trial therapy. If there is any question that a patient will not reliably comply with the requirements for contraception, that patient should not be entered into the study.

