7.6.2 Use in Pregnancy

If a patient inadvertently becomes pregnant while on treatment with Pembrolizumab (MK-3475), the patient will immediately be removed from the study. The site will contact the patient at least monthly and document the patient's status until the pregnancy has been completed or terminated. The outcome of the pregnancy will be reported without delay and within 24 hours if the outcome is a serious adverse experience (*e.g.*, death, abortion, congenital anomaly, or other disabling or life-threatening complication to the mother or newborn). The study investigator will make every effort to obtain permission to follow the outcome of the pregnancy and report the condition of the fetus or newborn. If a male patient impregnates his female partner, the study personnel at the site must be informed immediately and the pregnancy reported and followed.

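### Section 11.5 ends mandatory pregnancy reporting at 90 days after the last dose, 30 days before the protocol's own 120-day contraception window closes

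*Combined protocol and SAP*

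**What the plan says.** **Reporting.** Section 11.5 routes pregnancies and their outcomes through CTEP-AERS with a dedicated form. It then sets the window: a pregnancy in a patient or partner "from the time of consent to 90 days after the last dose of study drug must be reported and then followed for outcome". Newborns are to be followed to 30 days of age.

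**Contraception.** The protocol gives a 120-day limit four times:

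- Section 3.1.12, female patients: "for the course of the study through 120 days after the last dose of study medication".
- Section 3.1.12, male patients with female partners of childbearing potential: "starting with the first dose of study therapy through 120 days after the last dose of study therapy".
- Section 7.6.1, both sexes, avoidance of pregnancy: "while receiving study drug and for 120 days after the last dose of study drug".
- Section 7.6.1, again, after patients are told of unknown risks to the fetus: "throughout the study period up to 120 days after the last dose of trial therapy".

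The reason stands at the start of 7.6.1: "Pembrolizumab (MK-3475) may have adverse effects on a fetus in utero". The same section warns of fetal harm from cytarabine and advises against pregnancy with either anthracycline.

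**Related rules.** In 7.6.2, removal from study and monthly contact apply to a patient who becomes pregnant during pembrolizumab treatment. A further sentence in 7.6.2 asks for pregnancies in male patients' partners to be reported and followed, with no time limit. Section 7.3 requires CTEP to be told of a confirmed pregnancy in a participating patient, also with no post-dose limit.

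**The concern.** The protocol asks patients to avoid pregnancy for 120 days after the last dose because of possible harm to a fetus, but its dedicated reporting section stops at 90 days. No reason is given for the difference. A site that follows 11.5 exactly has no duty under that section to report a pregnancy conceived on, say, day 100, or to follow it to outcome, although it arose while the patient was still under the contraception requirement.

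What is at stake is safety information on a combination that includes an investigational use of pembrolizumab. Pregnancies will be few, so each followed outcome counts. Normal outcomes matter as well as abnormal ones, because without them an isolated abnormal report cannot be interpreted.

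**Working it through.** The documents state no figure for this gap, so there is none to reproduce. The check compares the stated windows.

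**Inputs**

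| Rule | Section | Who | End of window after last dose |
|---|---|---|---|
| Reporting and outcome follow-up | 11.5 | Patient or partner | 90 days |
| Contraception | 3.1.12 | Female patients | 120 days |
| Contraception | 3.1.12 | Male patients with female partners | 120 days |
| Avoidance of pregnancy | 7.6.1 (twice) | Both sexes | 120 days |
| Removal and monthly contact | 7.6.2 | Patients | During pembrolizumab treatment only |
| Partner pregnancy reported and followed | 7.6.2 | Partners of male patients | None stated |
| Notification of CTEP | 7.3 | Participating patients | None stated |

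**Step 1: length of the gap.** 120 − 90 = 30 days, that is, days 91 to 120. This reads 11.5 as referring to when a pregnancy begins. A pregnancy conceived by day 90 and recognised later is still covered.

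**Step 2: share of the post-dose window.** 30 / 120 = 25%.

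**Step 3: dependence on the denominator.** The avoidance period in 7.6.1 also includes time on treatment. Two illustrations, with assumed treatment lengths taken from Section 7.1:

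- Induction only, 35 days: 30 / (35 + 120) = 30 / 155 = 19%.
- Induction, four 28-day consolidation cycles and two years of maintenance: 35 + 4 × 28 + 730 = 877 days; 30 / (877 + 120) = 30 / 997 = 3%.

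The 25% is thus a share of post-dose days. None of these figures is a share of expected pregnancies.

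**Step 4: do other sections cover days 91 to 120?**

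- *Partners of male patients.* The undated sentence in 7.6.2 can be read to cover them, including follow-up. The planned enrollment in 10.2 is 24 + 4 = 28 men and 19 + 3 = 22 women, so this matters for a sizeable part of the trial.
- *Patients.* Section 7.3 may reach them if participation includes post-treatment follow-up. It sits among the reasons for stopping treatment, however, and it requires notification, not follow-up to outcome.
- *Infants.* Section 11.3.3 counts a congenital anomaly as serious, and its first footnote requires reporting beyond 30 days when the event is at least possibly attributed to treatment. This works only once the site knows of the event. It does not require the pregnancy to be followed.

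What remains most clearly uncovered is the reporting and active follow-up of patients' own pregnancies conceived after treatment ends.

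**Step 5: which last dose?** Section 11.5 counts from the last dose of study drug. Section 10.5.1.2 glosses that term as pembrolizumab. On that reading the 11.5 window has no starting point in the control arm, whose patients receive cytarabine and an anthracycline. The contraception rules variously say study drug, study medication, study therapy and trial therapy.

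**The case against.** Several points can fairly be made on the other side.

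**The gap is not total.** A reader might infer that no pregnancy in days 91 to 120 would be reported and that its outcome would be lost. The documents do not support that. The opening sentence of 11.5 and the sentences in 7.3 and 7.6.2 carry no date limit, and 11.3.3 gives a route for a possibly related anomaly. This stands, and it narrows the point. It does not remove it: 11.5 is the section that defines the duty, the system and the form, and it alone sets a post-dose limit. Undated sentences beside a dated one leave sites free to reach different answers.

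**120 days is a contraception period.** A reader might also infer that the protocol declares 120 days to be the period of fetal risk. It does not say so, and it gives no pharmacological basis for the number. The link to fetal harm is an inference from the rationale beside the rule. A precautionary contraception period and a reporting period need not be equal in principle. But where they differ, the plan should say why, and this one does not.

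**90 days may be a network rule.** Section 11.5 refers to NCI reporting guidelines that are not part of the documents, so this cannot be checked. If true, it would explain the difference without reconciling it with this protocol's own 120 days.

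**Few events are likely.** This stands. In 50 patients receiving intensive chemotherapy the expected number is small, which limits the weight of the point.

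**Conclusion.** The inconsistency is in the current text. Mandatory reporting and outcome follow-up under 11.5 end 30 days before the 120-day pregnancy-avoidance window in 3.1.12 and 7.6.1, leaving the last 25% of the post-dose days outside the only section with an explicit post-dose reporting limit. Because other sections may capture partner pregnancies, some notifications to CTEP and possibly related anomalies, the firm part of the finding is confined to patients' own pregnancies conceived after treatment ends.

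The conclusion rests on two readings: that 11.5 refers to when a pregnancy begins, and that its dated sentence governs over the undated ones elsewhere. It needs no assumption about event rates. It is a minor safety-reporting inconsistency, with no bearing on the primary endpoint, sample size or power.

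**What to change.** 1. In 11.5, extend the reporting and outcome follow-up window to match the protocol's stated 120-day contraception window, for patients and partners alike. If there is a reason to keep 90 days, state it there.
2. In 11.5, name the last dose from which the window runs in each arm, so that it is defined for control patients.
3. In 7.3 and 7.6.2, add a cross-reference to 11.5 for reporting and follow-up. Do not put a time limit on the partner sentence in 7.6.2, which is now open-ended. Do not extend the removal rule in 7.6.2 to patients who are already off treatment.

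Suggested wording for 11.5: *A pregnancy that begins in a patient or a patient's partner between consent and 120 days after the anchor dose is to be reported and followed to outcome. The anchor dose is [agent to be named] in the pembrolizumab arm and [agent to be named] in the control arm. Partner pregnancies reported under Section 7.6.2 are not subject to this limit.*

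The contraception requirement itself does not change. The cost is a short amendment and an update to the pregnancy form instructions. No visit or test is added, since Section 7.4 already provides for contact at least every six months.

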11.6 Secondary Malignancy

A *secondary malignancy* is a cancer caused by treatment for a previous malignancy (e.g., treatment with investigational agent/intervention, radiation or chemotherapy). A secondary malignancy is not considered a metastasis of the initial neoplasm.

CTEP requires all secondary malignancies that occur following treatment with an agent under an NCI IND/IDE be reported expeditiously via CTEP-AERS. Three options are available to describe the event:

- Leukemia secondary to oncology chemotherapy (e.g., AML)
- Myelodysplastic syndrome (MDS)
- Treatment-related secondary malignancy

Any malignancy possibly related to cancer treatment (including AML/MDS) should also be reported via the routine reporting mechanisms outlined in each protocol.

11.7 Second Malignancy

A second malignancy is one unrelated to the treatment of a prior malignancy (and is **NOT** a metastasis from the initial malignancy). Second malignancies require **ONLY** routine AE reporting unless otherwise specified.

12. STUDY CALENDAR

Screening evaluations are to be conducted within 21 days prior to start of protocol therapy. Blood tests will be taken at every clinic visit for 1 year (if applicable, drawn when routine blood samples are taken). In the event that the patient’s condition is deteriorating, laboratory evaluations should be repeated within 48 hours prior to initiation of the next cycle of therapy.

		Induction Phase											Consolidation Phase ^a								Maintenance / Observation Phase [£]	After 6 Months of Treatment	After 1 Year of Treatment	End of Maintenance / Observation ^b	Post-treatment Follow-Up ^c				
	Screening ^y	D1	D2	D3	D4	D5	D6	D7	D8	D9	D14	D28	Cycle 1				Cycles 2 ^a , 3, 4												
													D1	D3	D5	D28	D1	D3	D5	D28									
Cytarabine ^d		X	X	X	X	X	X	X			X ^e		X	X	X		X	X	X										
Daunorubicin or Idarubicin ^d		X	X	X							X ^e																		
Pembrolizumab (MK-3475) ^f									Every 3 weeks starting on Day 8 of the Induction phase																				
Informed Consent	X																												
Eligibility Criteria	X																												
Medical History, Demographics	X																												
Prior and Concomitant Medication Review		X.....X																											
Survival Status																								X					
EKG ^w	X																												
Physical Exam	X	X									X	X ⁿ			X					X	X			X					
Vital signs	X	X									X	X ⁿ			X					X	X			X					
Height	X																												
Weight	X																												
Performance Status ^g	X											X ⁿ			X					X	X			X					
Adverse event evaluation			X.....X																										
Comprehensive Chemistry Panel ^{h,v}	X	X	X	X	X	X	X	X	X ^o	X ^o	X	X ⁿ	X			X	X			X	X ^v			X					

	Screening ^y	Induction Phase											Consolidation Phase ^a								Maintenance / Observation Phase [£]	After 6 Months of Treatment (+/- 14 days)	After 1 Year of Treatment (+/- 14 days)	End of Maintenance / Observation ^b	Post-treatment Follow-Up ^c			
		D1	D2	D3	D4	D5	D6	D7	D8	D9	D14	D28	Cycle 1				Cycles 2 ^a , 3, 4											
													D1	D3	D5	D28 ^β	D1	D3	D5	D28 ^β								
CBC with Differential ^{h,v}	X	X	X	X	X	X	X	X	X	X	X	X ⁿ	X			X	X			X	X ^v				X	X		
Pregnancy Test ^l – Urine or Serum β-HCG	X																											
Urinalysis	X	X								X	X ⁿ				X				X	X								X
TSH; T3, T4 ^k	X							X		X										X								
PT, PTT, fibrinogen								X	X																			
Bone marrow ^l Aspiration	X									X ^m	X ⁿ				X				X ^o	X ^p	X	X		X ^s				
Bone marrow biopsy	X										X ⁿ				X				X ^o		X	X		X ^s				
Stool	X														X ^z													
Research Blood Draws	X									X ^m	X ⁿ				X				X ^o	X ^q	X ^r	X ^r		X ^s				
Skin Punch Biopsy ^α	X																											
Transthoracic ECHO (TTE) or MUGA	X								X ^t																			
CT chest	X ^s																											

- a If the patient does not have a CR/CRi before starting this part of the study, the patient should go off study. Patients <65 may complete 3-4 cycles of consolidation therapy. Patients ≥65 years old may complete 1-2 cycles of consolidation therapy.
- b End of treatment visit will be immediately following final dose of Pembrolizumab (MK-3475).
- c After completing study treatment, clinical follow-up assessments are required every 6 months from date of therapy discontinuation. Common clinical practice should be monitored by institutional practice (*i.e.*, every 3 months though not required by protocol), but assessment results are only required every 6 months (+/- 14 days). All participants should be followed for survival to 3 years after end of treatment. For patients who achieve undetectable MRD during study treatment, central MRD assessments should continue in addition to general clinical follow.
- d Cytarabine should be dosed as appropriate for each phase of the study. Daunorubicin (60 mg/m²/day) or Idarubicin (12 mg/m²/day)
- e If patient has residual leukemia at the time of bone marrow aspiration, the patient may receive a 5+2 administration of these drugs. Adjust anthracycline dose as per institutional standards for Re- Induction.
- f Only for patients randomized to Arm B at 200 mg. Pembrolizumab (MK-3475) will be administered on Day 8 of induction and then Q3 weeks (+/- 3 days). Do not administer pembrolizumab concurrently with HIDAC chemotherapy Days 1-5 of each consolidation cycle. For consideration of timing of pembrolizumab, allow at least 3 hours after completion of chemotherapy prior to pembrolizumab administration. Administration window for pembrolizumab may be extended to allow for this timing as necessary. Each cycle of Maintenance is 21 days with pembrolizumab given on day 1 of each cycle up to 2 years.
- g Note: Performance status evaluations are based on a 4-week cycle. At minimum, performance status should be evaluated at the beginning of every cycle.
- h Albumin, alkaline phosphatase, total bilirubin, bicarbonate, BUN, calcium, chloride, creatinine, glucose, LDH, phosphorus, potassium, total protein, SGOT [AST], SGPT [ALT], sodium.

NCI Protocol #: 10300

Version Date: April 10, 2025

- i CBCs (with differential and platelet count), which includes WBC, ANC, platelets, Hgb, and Hct required for protocol therapy must be done <24 hours prior to the treatment cycle.
- j For women of childbearing potential, a serum or urine pregnancy test must be conducted within 72 hours prior to first dose of study treatment on both Arm A and Arm B. If the urine test is positive or cannot be confirmed as negative, a serum pregnancy test will be required.
- k TSH should be performed at baseline and <72 hours prior to each dose of Pembrolizumab (MK-3475). Additional T3 and T4 tests should be performed as clinically indicated, if TSH is abnormal, if symptoms are suggestive of thyroid dysfunction.
- l Bone marrow aspirate is required to be submitted for central MRD testing as outline in Section 5. Submit to [name] lab at Children's Hospital Los Angeles. Results will be forwarded to the submitting institution within 1-2 business days of receipt of the bone marrow aspirate samples. Local bone marrow biopsy (aspirate) must be performed at the indicated time points and should follow the institutional standard of care.
- m To be collected between Day 14 and Day 21.
- n To be collected between Day 28 and Day 42.
- o To be collected at the end of consolidation therapy only.
- p Bone marrow aspirations every 3 months during maintenance/observation phase are optional and should only be collected when part of standard of care.
- q To be collected every 3 months during maintenance phase.
- r Blood collection for the immune cell subset analysis and Olink assay only.
- s Bone marrow aspiration and blood should be collected for MRD status in patients who have not relapse. For patients who have relapsed, bone marrow core biopsies, bone marrow aspirate, and blood should be collected. Blood collection for cfDNA will be obtained at the same time-points as blood collection for MRD status.
- t Repeat TTE should be performed before 5+2 reinduction.
- u PT, PTT, and fibrinogen will be additionally collected on days 8 and 9 (pre- and post-) in the pembrolizumab arm.
- v CBC and CMP will be obtained within 3 days of receipt of each pembrolizumab dose in the pembrolizumab arm and every 3 weeks during treatment and every 6 (+/- 1 week) weeks during observation for patients in the control arm.
- w ECGs performed after screening will be done as medically indicated.
- x CT chest should be considered as a part of screening (optional)
- y Screening period is up to 21 days
- z At time of Post-Consolidation Cycle 1 bone marrow collection (+/- 3 days)
- α Refer to Section 5.1 Summary Table for Specimen Collection and Appendix F Skin Punch Biopsy Verification Form
- β (+/- 3) days
- £ Observation visits in Maintenance on control arm may be extended to 6 weeks (+/- 1 week).

